- a) Dapagliflozin causes a rapid and significant reduction of EAT in type 2 diabetic patients
- b) Dapagliflozin-induced EAT reduction would be associated with a significant reduction of LV mass, independent cardiovascular risk factor.

ENDPOINTS:

Primary Endpoint: EAT (Epicardial fat thickness) will be measured with echocardiography according to the method described and validated by [name] et al. Full description of the measurement is reported in the section "Methodology"

Secondary Endpoint: LVM (left Ventricular Mass) will be measured with echocardiography according to the standard formula, fully described in the section "Methodology"

SPECIFIC OBJECTIVES

Primary Objective:

- a) Does treatment with Dapagliflozin cause a significant decrease in EAT in subjects with type 2 diabetes?

Secondary Objective:

- b) Does treatment with Dapagliflozin cause a significant decrease in LVM, through the reduction of EAT, in subjects with type 2 diabetes?

[figure not shown]
STUDY DESIGN

This will be an interventional, double-blind, parallel group, placebo controlled study in 100 overweight/obese type 2 diabetic subjects who are taking Metformin as monotherapy.

Individuals will be randomized in two groups of 50 patients, to receive additional Farxiga (Dapagliflozin) (F-group) or to remain on Metformin (M-group) plus placebo orally once daily.

[figure not shown]
- F-group: Dapagliflozin will be administered at the starting dose of 5 mg once daily, then if no safety issues will occur, it will be titrated up to 10mg once daily after 2 weeks. Metformin (from 500 mg twice daily to a maximum of 1000 mg twice daily) regimen will be continued to achieve fasting glucose between 80 and 140 mg/dl.
- M-group will be treated with Metformin plus placebo orally once daily for the duration of the study. Metformin (from 500 mg twice daily to a maximum of 1000 mg twice daily) regimen will be continued to achieve fasting glucose between 80 and 140 mg/dl.

Both groups will receive lifestyle and diabetes education, as part of the standard care.

STUDY TIMETABLE

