Participants will be scheduled for the first visit (visit 0) after an overnight fast. Patients will be randomly assigned to receive Farxiga 5 mg or placebo once daily. After 2 weeks patients will receive detailed instructions over the phone to titrate Farxiga or placebo up to 10 mg once daily. F- and M- group patients will undergo clinical examination, anthropometrics, transthoracic echocardiogram for EAT and LVM measurement and point of care (POCT) of fasting glucose and haemoglobinA1c (HbA1c) and estimated Glomerular Filtration Rate (eGFR) at each visit, baseline (visit t0), 3 (visit t3), and 6 months (visit t6)

STUDY POPULATION

Number of subjects to be studied: One hundred overweight/obese type 2 diabetic subjects.

Planned number of subjects to be screened: Five hundred subjects will be screened among the outpatient population who routinely refer to [name] of Miami Diabetes Clinic at the Diabetes Research Institute (UMMG-DRI), out-patient clinics. [name] visits approximately 2000 diabetic patients per year.

Anticipated number of trial sites: UMMG-DRI out-patient diabetes clinics, University of Miami.

INCLUSION CRITERIA

- Type 2 diabetes, as defined by ADA criteria
- HbA1c < 8% measured at least 1 week prior to the study
- BMI ≥ 27 kg/m²
- Pre-treatment with Metformin as monotherapy
- Age > 18 and < 65 years old
- Normal and stable hemodynamic status

EXCLUSION CRITERIA

- Known contra-indications to Farxiga, in accordance with risks and safety information included in the latest updated Prescribing Information
- Type 1 diabetes, as defined by American Diabetes Association (ADA) criteria
- Insulin dependent or treated type 2 diabetes
- Current use of other SGLT2 inhibitors, GLP- 1 analogs or DPP4 inhibitors
- Glomerular Filtration Rate (GFR) < 60 mL/min/1.73 m²
- Signs or symptoms of hypovolemia
- Patients with poor glycemic control (HbA1c ≥ 8%) will be excluded to maximize long-term patient retention without need
- History of diabetes ketoacidosis
- Patients with active bladder cancer or with a prior history of bladder cancer
- Acute or chronic infective, including genital mycotic infections
- Clinical signs or symptoms of New York Heart Association (NYHA) class III-IV heart failure
- Clinical or laboratory evidences of chronic active liver diseases
- Acute or chronic infective diseases
- Cancer or chemotherapy
- Current use of systemic corticosteroids or in the 3 months prior this study

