We expect that Dapagliflozin will cause a significant decrease in EAT, but much smaller when compared to weight loss interventions such as a VLCD. EAT decrease has been shown to vary (between -12% and -32%) after different interventions. EAT reduction is anticipated to be between -15% and -25% after 3 months of treatment with Dapagliflozin. A hypothesis of at least 15% reduction in EAT is based on: a) the previously reported weight-loss caused by Dapagliflozin, b) previously-reported responsiveness (decrease) of EAT to pharmacological agents targeting the fat. A reduction of 15%, an absolute difference of 1.2 mm from baseline, will be considered not only statistically, but clinically significant of visceral fat reduction. It is worthwhile to note that a reduction of 0.4 and 1.4 mm in EAT after atorvastatin and bariatric surgery, respectively, was previously considered statistically and clinically significant. However, it is possible to expect a larger difference after 6 months of treatment

Given the reference value and the expected difference in EAT, the statistical power of the study (two-sided, $\alpha=0.05$) was calculated.

Outcome	Reference value \pm SD	Expected Difference	Detectable difference with 80% power $\alpha=0.05$	Detectable difference with >99% power $\alpha=0.05$
EAT (mm)	8 ± 3	-15-or -25%	-15% (absolute difference = 1.2)	-25% (absolute difference = 2)

A convenience sample of 50 individuals for each group will therefore provide the statistical power (80%) to detect an expected difference of -15% in the EAT before and after treatment with Dapagliflozin. Baseline SD of 3 is expected to lower to approximately 2 for the expected change. The expected change of SD will assure significant statistical power of the comparative test.

Study Hypothesis 1 Dapagliflozin causes a significant and rapid decrease in EAT. Comparative statistical analysis between F and M-group will be performed to tests this hypothesis. Continuous variables will be considered as age-adjusted and sex-adjusted means with their standard deviations (SDs). Two-tailed $p < 0.05$ indicates statistical significance. ANOVA model with adjustment for baseline will be used to calculate the changes (Δ) in EAT between baseline, 3 and 6 months in both F and M-group.

Study Hypothesis 2

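### The plan names a between-arm test for the primary endpoint EAT, but not the visit or model contrast that decides it, and the power sentence describes a within-arm change

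*Combined protocol and SAP*

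**What the plan says.** Under Endpoints, the primary endpoint is EAT by echocardiography, with no visit, change measure or contrast. The primary objective asks "Does treatment with Dapagliflozin cause a significant decrease in EAT in subjects with type 2 diabetes", again without a visit or a comparator. The Study Timetable schedules the echocardiogram at baseline, month 3 and month 6.

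The Statistical Considerations section supplies part of what is missing. For Study Hypothesis 1, "Comparative statistical analysis between F and M-group will be performed to tests this hypothesis". The model is an ANOVA adjusted for baseline, applied to changes "in EAT between baseline, 3 and 6 months in both F and M-group", with age- and sex-adjusted means and two-tailed significance at 0.05. No section gives a multiplicity rule.

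On timing, "EAT reduction is anticipated to be between -15% and -25% after 3 months of treatment with Dapagliflozin", and the hypothesis speaks of a *rapid* decrease. The same paragraph adds: "However, it is possible to expect a larger difference after 6 months of treatment".

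On power, the table gives EAT as 8 ± 3 mm, with 80% power for 1.2 mm (defined as a change from baseline) and more than 99% for 2 mm. The text says that 50 per group gives 80% power "to detect an expected difference of -15% in the EAT before and after treatment with Dapagliflozin". The sentences that follow expect the SD to drop from 3 to about 2 for the change, and say that this secures the power of the comparative test.

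**The concern.** Two post-baseline visits and several model terms could each be called the result for Hypothesis 1, and nothing in the plan picks one. The choice could therefore be made after the data are seen. A trial that is significant at one visit and not at the other would have no pre-stated answer, and a reader could not check which test had been intended.

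The power sentence adds to the uncertainty. A before/after change in the F-group is a different quantity from the F-M difference. It does not isolate the drug, because "Both groups will receive lifestyle and diabetes education, as part of the standard care", so EAT may fall in both arms. If the power was worked out for the before/after change, it does not describe the test that decides the hypothesis.

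**Working it through.** **1. The plan's own power figures.** Inputs from Statistical Considerations: differences 1.2 and 2 mm, SD 3 (table) or about 2 (text, for the change), 50 per arm, two-sided 0.05. Attrition below 10% (Compliance and Retention Strategy) leaves at least 50 × 0.9 = 45 per arm. Power is from the noncentral t, with noncentrality δ/(SD/√n) for one arm before/after and δ/(SD·√(2/n)) for F-M.

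| Test | n per arm | SD | 1.2 mm | 2 mm |
|---|---|---|---|---|
| One arm, before/after | 50 | 3 | 1.2/(3/√50) = 2.83: 79.2% | 4.71: 99.6% |
| F-M | 50 | 3 | 1.2/(3·√(2/50)) = 2.00: 50.8% | 3.33: 91.0% |
| F-M | 50 | 2 | 3.00: 84.4% | 5.00: 99.9% |
| F-M | 45 | 2 | 2.85: 80.4% | 4.74: 99.7% |

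The stated 80% and >99% fit a one-arm test with the tabled SD, and also lie close to an F-M test with SD 2. They do not fit an F-M test with SD 3. The table therefore does not show which test was meant. The F-M rows treat 1.2 mm, which the plan defines as a change from baseline, as the difference between arms; that assumes no change in the M-group.

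**2. Error rate if either visit may succeed.** The documents give no visit-to-visit correlations, so these are assumed. The correlation of baseline with follow-up is rb = 0.6 to 0.78; the upper value follows from 1 − 2²/(2·3²) = 0.78 if the SD of change is 2 and the follow-up SD is 3. The correlation of month 3 with month 6 is r36 = 0.7 to 0.9, taken to be at least rb. With the same rb at both visits, the two baseline-adjusted F-M tests have correlation

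ρ = (r36 − rb²)/(1 − rb²),

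and the two-sided error is 0.05 + 0.05 − P(both significant), from the bivariate normal with cut-off 1.96.

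- Lowest: rb 0.6, r36 0.9. ρ = (0.90 − 0.36)/0.64 = 0.84; 0.10 − 0.025 = 7.5%.
- Highest: rb 0.7, r36 0.7. ρ = (0.70 − 0.49)/0.51 = 0.41; 0.10 − 0.007 = 9.3%.
- With rb 0.78, r36 of 0.78 and 0.9 give 9.2% and 8.1%.

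The rate of a false claim of benefit is 3.8% to 4.7%, against 2.5% for one visit. The ceiling for two independent tests is 1 − 0.95² = 9.75%. Simulating the baseline-adjusted analysis with 50 per arm (60,000 runs for each of the eight correlation pairs) gave 7.5% to 9.3% for either visit and 4.9% to 5.1% for a single visit.

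**3. What splitting alpha would cost.** Assume 1.2 mm F-M at both visits, 50 per arm and residual SD = 3·√(1 − r²), where r is the correlation with baseline. This SD is 1.89 for r 0.78 and 2.40 for r 0.6.

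- Power at one given visit falls from 88% (at 0.05) to 82% (at 0.025) for r 0.78, and from 70% to 59% for r 0.6.
- Power to succeed at either visit at 0.025 (normal approximation) is about 90% to 94% for r 0.78, against 89% for one visit at 0.05. For r 0.6 it is 69% to 76%, against 70%.

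**The case against.** The plan does name a test. Study Hypothesis 1 is to be judged by comparing F with M, in one ANOVA adjusted for baseline. A single overall group term or group-by-time term fits that wording as well as two separate visit tests do, and a single test has no inflation. Month 3 is also a fair inference from the planning effect and from the word *rapid*. These points stand, and they limit the finding to the missing visit and contrast. They do not remove it: the plan never says that the omnibus term decides, and the planning text points to month 3 while leaving room for a larger effect at month 6.

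On power, the sentences after the before/after statement tie the SD of about 2 to the comparative test. That also stands. A reader might infer from the power sentence that a fall within the F-group alone could meet the primary hypothesis. The documents do not support this: the objective names no comparator, but the statistical section says that the hypothesis is tested between the groups. The before/after wording is a mismatch to correct and does not amount to a second route to success.

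**Conclusion.** The concern holds: the deciding visit and contrast for the sole primary endpoint are not fixed, so the plan as written does not secure its stated 5%. The 7.5% to 9.3% is conditional on an either-visit rule, which no section states, and on assumed correlations. A reader might infer that the trial's error rate *is* 9%; the text supports only that it is left uncontrolled. One named visit or one omnibus test would hold 5%, and requiring both visits would give less.

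A reader might also infer that the trial is underpowered. That does not follow. With the SD of change of about 2 that the plan expects, F-M power for 1.2 mm is 84% at 50 per arm and 80% at 45. It drops to about 51% only if the tabled SD of 3 applies to the comparison. What is established is that the power sentence describes a different quantity from the test. The omission is certain; the sizes depend on the assumptions shown.

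**What to change.** Before any outcome is compared by arm, add a paragraph to this effect: *The primary test is the F-M difference in EAT at month 3, adjusted for baseline EAT, age and sex, at two-sided alpha 0.05, from one repeated-measures model with group, visit and group-by-visit. The month-6 F-M difference from the same model is tested at 0.05 only if month 3 is significant. Within-arm changes are descriptive.* Month 3 is suggested because the planning effect and the word *rapid* refer to it. Naming month 6, one omnibus group term, or 0.025 per visit would also control the error; the essential step is to fix one. Add the visit and comparator to the primary endpoint and objective as well.

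Restate the power for the F-M difference, giving the assumed SD of change (about 2), the number expected after attrition, and the assumed change in the M-group.

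The cost is one paragraph, with no extra patients or visits. Under the fixed order, a result significant only at month 6 becomes secondary. If that is unwelcome, splitting alpha keeps month 6 eligible. It lowers power at each single visit, but if the effect is 1.2 mm at both visits, the chance of succeeding at one or the other is similar or higher (about 2 points lower at worst).

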Dapagliflozin is a new and emerging anti-diabetes medication. Dapagliflozin is a selective sodium-glucose cotransporter 2 (SGLT2) inhibitor, reduces hyperglycemia in patients with type 2 diabetes mellitus (T2DM) by increasing urinary glucose excretion, and weight loss is a consistent associated finding. Because dapagliflozin increases urinary glucose excretion, weight loss could result from reduced body fat secondary to caloric loss or from fluid loss secondary to osmotic diuresis or from a combination of both factors. Nevertheless, whether Dapagliflozin may cause a reduction in visceral fat is unknown. Also whether Dapagliflozin can reduce EAT, visceral fat of the heart, and improve cardiac performance, is unexplored.

Hence, in this study we would like to test the hypotheses that Dapagliflozin (a) causes a rapid and significant reduction of EAT, as marker of visceral fat, in type 2 diabetic patients, (b) Dapagliflozin-induced EAT reduction is associated with a significant reduction of LVM. These hypotheses would be tested in an interventional, double-blind, parallel group, placebo controlled study in 100 overweight or obese type 2 diabetes subjects.

This proposal therefore contains a number of novel concepts and an innovative methodology with immediate and important clinical application.

Key words: visceral fat; epicardial fat; Dapagliflozin; type 2 diabetes

Background

Visceral Fat and Cardiovascular Risk

[figure not shown]
Different body fat distribution has been clearly associated with different cardiovascular risk. A number of evidences indicate that subjects with excess visceral fat accumulation are at higher risk for cardio-metabolic diseases and diabetes. Traditionally, most of the attention has been focused to the intra-abdominal visceral fat accumulation and waist circumference has been largely used as surrogate marker of visceral adiposity. However, waist circumference may provide incomplete information or be subject to operator variability. Imaging studies, as well as MRI or computed tomography are certainly more accurate estimates of body visceral fat content, but more costly and invasive. With this in mind, I have focused my attention to an emerging visceral fat depot, the epicardial fat, and developed a methodology through which epicardial fat can be visualized and measured using standard two-dimensional echocardiography with several advantages, including its low cost, easy accessibility and good reproducibility

Epicardial Fat

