Increased visceral fat is an established risk factor for a poor cardiometabolic profile. Type 2 diabetes is frequently accompanied with excessive visceral fat accumulation. Dapagliflozin has shown to improve glucose control and induce weight loss in subjects with type 2 diabetes. Whether the weight loss effect of Dapagliflozin is characterized by a rapid reduction in visceral fat is unknown, but it would be great clinical relevance. Recently it has been suggested that Dapagliflozin can cause weight loss and improve cardio-metabolic profile beyond the glycemic control. Whether this effect can be also explained by a reduced visceral fat is unexplored. Whether Dapagliflozin can reduce the risk of LVH and ultimately heart failure is unknown. Achieving this knowledge may be of great importance in the management of overweight/obese type 2 diabetic subjects at higher cardiovascular risk. Given the poor accurateness and sensitivity of the traditional anthropometric markers of intra-abdominal fat, such as BMI and waist circumference, there is a great scientific effort in finding reliable and easy markers of the visceral, organ-specific adiposity. We already showed that EAT, as measured with echocardiography, precisely reflects visceral adiposity and rapidly changes during medical interventions targeting the fat. If our hypothesis is true, EAT can serve as simple and non invasive marker of visceral fat loss during therapy with Dapagliflozin. This proposal therefore contains a novel concept and an innovative methodology with immediate and important clinical application

HYPOTHESIS OF THE STUDY

In this study we would like to test the hypothesis that Dapagliflozin may improve cardio-metabolic profile through a direct effect on an easily-accessible organ-specific visceral fat.

STUDY HYPOTHESES

1. We hypothesize that Dapagliflozin can induce a significant and rapid decrease in EAT, as marker of visceral adiposity. Given the rapid metabolism of EAT and its capacity to significantly decrease with agents targeting the fat, as previously reported, we hypothesize that EAT can be significantly changed during treatment with Dapagliflozin.
2. We previously showed that EAT significantly and independently correlate with LVM. We also showed that EAT reduction was independently associated with reduction in LVM. Given these findings, we hypothesize that Dapagliflozin can reduce LVM through an effect on EAT.

SPECIFIC AIMS

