Dapagliflozin reduces LVM through an effect on EAT. Based on our previous data (36) we know that LVM reduction is independently related to epicardial fat reduction. We hypothesize that LVM will reduce in the F-group and better than in the M-group. ANOVA test with 95% CI will be used to calculate the changes (Δ) in study parameters between baseline, 3 and 6 months in both F and M-group. Relations between Δ epicardial fat, Δ BMI, Δ waist circumference and Δ LVM will be calculated using simple linear regression analysis. Variables with a $p < 0.1$ value on univariate analysis will be entered in different multivariate analysis models to assess the independent determinants of Δ LVM, as dependent variables. Echocardiographic epicardial fat will be compared to BMI, waist circumference and to waist-hip ratio as independent predictor of Δ LVM. The optimum sensitivity and specificity of threshold values of EAT to predict reduction in LVM will be examined by receiver operating characteristics (ROC) analysis by plotting sensitivity vs. 100 – specificity.

DATA HANDLING AND RECORD KEEPING:

Data Collection: Each of the dedicated clinic exam rooms at the UMMG-DRI provides direct access to the clinical research study electronic data capture (EDC) eVelos system provided by the Clinical Research Informatics and Data Management Unit of the Center for Health Informatics and Bioinformatics at UM. The sponsor investigator and research coordinator will collect and manage the data.

ETHICS:

Informed Consent

Eligible and willing participant will be contacted by the research coordinator and consented. Previous to the signing of the informed consent, extensive oral and written information will be given to the subjects, including information about risks associated with Dapagliflozin treatment (in accordance with the updated Prescribing Information) before initiating any study related activity.

Confidentiality of data The sponsor investigator will explain that participant confidentiality will be maintained, data will only be identified by a number and that their consent forms with identification number will be kept locked in a filing cabinet.

Protections against Risk

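### The randomised comparison can show whether dapagliflozin lowers LVM, but no planned analysis can show that it does so through EAT; the LVM models also leave out baseline LVM and treatment arm

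*Combined protocol and SAP*

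**What the plan says.** The combined protocol and SAP words the EAT–LVM link in two ways.

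- **Causal.** Under Study Hypotheses: "we hypothesize that Dapagliflozin can reduce LVM through an effect on EAT". The secondary objective asks whether treatment will "cause a significant decrease in LVM, through the reduction of EAT, in subjects with type 2 diabetes". Study Hypothesis 2 in the statistical section: "Dapagliflozin reduces LVM through an effect on EAT".
- **Associational.** The opening summary: "Dapagliflozin-induced EAT reduction is associated with a significant reduction of LVM". Specific Aim (b): "Dapagliflozin-induced EAT reduction would be associated with a significant reduction of LV mass".

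Study Hypothesis 2 plans four analyses:

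1. For LVM and the other parameters, "ANOVA test with 95% CI will be used to calculate the changes" from baseline to 3 and 6 months in both groups, with the expectation that LVM falls more in the F-group.
2. Simple regressions among the changes in EAT, BMI, waist and LVM.
3. Multivariable models: variables with a p below 0.1 "value on univariate analysis will be entered in different multivariate analysis models to assess the independent determinants of" LVM change. In addition, "Echocardiographic epicardial fat will be compared to BMI, waist circumference and to waist-hip ratio as independent predictor of" LVM change.
4. A ROC analysis of EAT thresholds for predicting LVM reduction.

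The reference to both groups belongs to the ANOVA sentence. The regression sentences name no treatment arm and no pooling rule. Study Hypothesis 1 adjusts the EAT ANOVA for baseline; the LVM ANOVA names no such adjustment, although Visit Procedures has LVM measured at baseline in every patient.

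**The concern.** A claim that a drug acts through an intermediate needs more than a treatment effect on each variable and a correlation between their changes. The plan defines no direct or indirect effect, no set of EAT–LVM confounders, and no time ordering of the 3- and 6-month changes. A significant EAT slope could therefore be reported as evidence of mechanism when it is not.

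Two gaps in specification add to this. If both arms are pooled and arm is left out, the treatment effect itself can create a correlation between EAT change and LVM change. And analysing LVM change without baseline LVM gives up precision on the only secondary endpoint, using a variable the trial already collects.

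**Working it through.** **The plan's own figures.** None is given for LVM or for the EAT–LVM link. The only power statement is for EAT: 80% for 1.2 mm with 50 per group. It reproduces as a before–after test in one group with SD 3: 1.2 / (3/√50) = 2.83; Φ(2.83 − 1.96) = 0.81. The 1.2 mm is thus a before–after change. Both arms receive lifestyle education, so the F–M difference may be smaller.

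**Inputs.** From the documents: 50 per arm, two-sided 0.05, and EAT changes of 1.2 and 2 mm with a change SD of about 2, giving 0.6 and 1.0 SD. Assumed: an EAT difference of 0.3 SD as a smaller case, and LVM shifts of 0.2, 0.4 and 0.6 SD.

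**Pooled single slope without arm, no EAT–LVM path.** With equal arms and shifts dE and dL in within-arm SDs, the pooled correlation is

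r = (dE·dL/4) / √[(1 + dE²/4)(1 + dL²/4)].

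With f = atanh(r)·√(100 − 3), the rejection rate is Φ(f − 1.96) + Φ(−f − 1.96).

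Example, dE = dL = 0.6: r = 0.09/1.09 = 0.083; f = 0.815; rate = Φ(−1.145) + Φ(−2.775) = 0.126 + 0.003 = 0.129.

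| F–M EAT difference | LVM shift 0.2 SD | 0.4 SD | 0.6 SD |
|---|---|---|---|
| 0.3 SD | 5% | 6% | 7% |
| 0.6 SD | 6% | 9% | 13% |
| 1.0 SD | 7% | 14% | 25% |

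Simulation agrees to within about half a percentage point. With arm in the model, or in the F-group alone, the simulated rate is about 5% throughout.

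**Multivariable models after the p < 0.1 screen, pooled without arm (simulated).** At EAT differences of 0.3, 0.6 and 1.0 SD:

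- EAT and BMI: 4–7%, 4–12%, 6–24% (assumed BMI shift 0.6–1.0 SD, correlation with EAT 0–0.3).
- EAT, BMI, waist and waist–hip ratio: 4–5%, 4–9%, 6–17% (assumed shifts 0.6, 0.4, 0.3 SD; correlation 0.3 with EAT, 0.6 with each other).

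**What arm adjustment cannot do.** Suppose an unmeasured factor drives both changes, giving a within-arm correlation ρ with no effect of EAT on LVM. With arm in the model, f = atanh(ρ)·√(100 − 1 − 3):

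- ρ = 0.1: f = 0.98, EAT significant in 17% of trials
- ρ = 0.2: f = 1.99, 51% (51–53% across simulations)
- ρ = 0.3: f = 3.03, 86%

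**Baseline LVM.** With equal variances and baseline–follow-up correlation r, a change score has variance 2σ²(1 − r) and ANCOVA has σ²(1 − r²). The ratio is (1 + r)/2: 0.75, 0.90 and 0.95 at r = 0.5, 0.8 and 0.9. An assumed 80% power corresponds to 1.960 + 0.842 = 2.802 standard errors. Dividing by √0.75, √0.90 and √0.95 gives 3.235, 2.953 and 2.874, hence power of 90%, 84% and 82%.

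**The case against.** The best defence is that the secondary objective first asks whether dapagliflozin lowers LVM, and the randomised F versus M comparison answers that. This stands. A reader might infer that the whole secondary objective is unanswerable; the documents do not support that, because only the clause about the route through EAT lacks an analysis. Nor is the LVM comparison biased by omitting baseline LVM: randomisation protects it either way.

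It is also fair to say that the inflation needs one reading the plan does not state, pooling without arm, together with LVM effects the documents do not give. Analysed by arm, there is none. At an EAT difference of 0.3 SD it is negligible, and with all four named predictors it is modest up to 0.6 SD. Where weight change drives both EAT and LVM, the planned EAT and BMI model already copes, with a false EAT finding in about 3% of simulated trials.

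The p < 0.1 screen might look like the culprit. It is not: screened and unscreened pooled models give nearly the same rates (8.7% and 8.7% in one setting, 17.6% and 16.9% in another). Leaving out arm is what matters.

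What remains is the mismatch between the causal wording and the analyses, the unstated pooling rule, and the missing baseline term.

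**Conclusion.** The point holds in this limited form and should be corrected before analysis. The causal wording is unsupported by anything planned, and the document's own summary and Aim (b) already contain wording the analyses can support. This part rests on the text alone.

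The sizes rest on assumptions. The false EAT slope is conditional on pooling without arm and on separate drug effects on EAT and LVM; the LVM shifts are assumed. The gain from baseline LVM depends on an assumed correlation and starting power.

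A reader might infer that adding arm would turn the regression into evidence of mechanism. It would not, since an unmeasured shared cause survives that adjustment. The wording has to change as well as the model. The primary EAT comparison is unaffected.

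**What to change.** 1. Analyse LVM at 3 and 6 months by ANCOVA with arm and baseline LVM, and report the F–M difference with its 95% CI.
2. State that the LVM-change regressions pool both arms and include arm as a covariate. Keep BMI change and waist change in the model used for any statement that EAT is an independent determinant.
3. Replace the causal wording with association in Study Hypotheses, the secondary objective and Study Hypothesis 2, and apply the same limit to the ROC analysis.

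Dropping the p < 0.1 screen and forcing in baseline EAT are optional.

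**Cost.** Every variable is already collected. Items 1 and 2 are analysis text; item 3 also amends the protocol's hypothesis and objective. The mechanistic claim becomes more cautious, and some power for a true EAT–LVM association is lost. For assumed within-arm slopes of 0.2, 0.3 and 0.4 SD per SD, an unscreened model with arm, BMI and waist change, and also baseline LVM and baseline EAT, detects the slope in 45, 80 and 97% of simulated trials. The pooled screened model without arm detects it in 48, 84 and 98%, and the F-group alone in 28, 57 and 83%. Pooling with arm is therefore preferable to splitting by arm.

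### The p < 0.1 univariate screen and unspecified models for LVM change can distort the reported EAT coefficient when effects are weak; one model named in advance avoids this

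*Combined protocol and SAP*

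**What the plan says.** The analysis is described in the combined protocol and SAP, Statistical Considerations, Study Hypothesis 2. It has three steps.

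- Simple regressions: "Relations between Δ epicardial fat, Δ BMI, Δ waist circumference and Δ LVM will be calculated using simple linear regression analysis".
- Selection and adjustment: variables with a p < 0.1 "value on univariate analysis will be entered in different multivariate analysis models to assess the independent determinants of" LVM change.
- Comparison: "Echocardiographic epicardial fat will be compared to BMI, waist circumference and to waist-hip ratio as independent predictor of" LVM change.

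The text gives no fixed covariate list, no number of models and no primary model. It does not say whether EAT stays in if it fails the screen. It names no term for treatment arm or baseline LVM. Adjustment for age and sex appears only under Study Hypothesis 1.

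The analysis serves the secondary objective: "Does treatment with Dapagliflozin cause a significant decrease in LVM, through the reduction of EAT, in subjects with type 2 diabetes"?

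**The concern.** The between-arm comparison of LVM can show whether LVM falls on dapagliflozin. It cannot address the part of the objective that says the fall runs through EAT. For that part the plan relies mainly on this regression.

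Changes in EAT, BMI and waist are likely to be correlated. If EAT must reach p < 0.1 before it is fitted with the others, its adjusted coefficient is seen mainly in trials where chance made it look strong, and the usual interval takes no account of that. A variable that matters only after adjustment may never be fitted. Leaving the set of models open also means that the plan does not say which EAT coefficient is the result.

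**Working it through.** **The plan's own figures.** The plan gives no power or error rate for this regression. Its only power figures concern EAT. They reproduce as a before-after test in 50 patients with SD 3: 1.2/(3/√50) = 2.83 and Φ(2.83 − 1.96) = 80.7%; 2/(3/√50) = 4.71 and Φ(4.71 − 1.96) = 99.7%. They have no bearing on this point.

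**Inputs from the plan.** "Individuals will be randomized in two groups of 50 patients", so 100 in all. Attrition is expected to be below 10% (Compliance and Retention Strategy), so at least 100 × 0.9 = 90 complete. The screen is p < 0.1; tests are two-sided at 0.05.

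**Assumptions.** The documents give no correlations or effects on LVM. I take standardised changes, a correlation of 0.5 between EAT change and BMI change, and the effects shown below.

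**Step 1: what the screen requires.** The threshold is r = t/√(t² + n − 2). With n = 90, 1.662/√(2.76 + 88) = 0.174; with n = 100 it is 0.165. By Fisher's z, a variable with true correlation 0.1, 0.2 or 0.3 with LVM change is dropped in 76%, 40% or 11% of trials at n = 90 (74%, 36%, 8% at n = 100). If EAT has no effect of its own, its correlation with LVM change is 0.5 × 0.15 = 0.075 or 0.5 × 0.20 = 0.10. It then passes in only about 18 to 25% of trials.

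**Step 2: the EAT coefficient when the truth is 0.** n = 90, 40,000 simulated trials per row. Each cell gives mean coefficient, coverage of the 95% interval, and share with p < 0.05.

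| BMI effect | EAT passes | Screened analysis, trials where EAT passes | BMI always kept, same trials | EAT always kept, BMI screened, all trials | Both always kept, all trials |
|---|---|---|---|---|---|
| 0.15 | 18.5% | 0.138, 79%, 21% | 0.135, 83%, 17% | 0.025, 95%, 5% | 0.00, 95%, 5% |
| 0.20 | 24.7% | 0.127, 85%, 15% | 0.124, 89%, 11% | 0.020, 95%, 5% | 0.00, 95%, 5% |
| 0.30 | 41.0% | 0.094, 93%, 7% | 0.093, 94%, 6% | 0.005, 95%, 5% | 0.00, 95%, 5% |
| 0.40 | 60.6% | 0.060, 96%, 4% | 0.060, 96%, 4% | 0.001, 95%, 5% | 0.00, 95%, 5% |

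Smaller runs of the first two rows gave coverage between 78% and 86%.

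**Step 3: where the bias comes from.** The third and fourth columns use the same trials, so they compare like with like. Dropping BMI moves the mean by 0.138 − 0.135 = 0.003 and 0.127 − 0.124 = 0.003, and costs 3 to 4 points of coverage. The rest comes from looking only at trials in which EAT passed.

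**Step 4: overall false positives.** The chance that EAT both passes and is significant is 0.185 × 0.21 = 3.9% in the first row and 0.247 × 0.15 = 3.7% in the second. It is about 3% with a BMI effect of 0.3.

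**Step 5: when EAT does have an effect.** With both effects at 0.3, the mean is 0.30 and coverage 95%, so there is no bias. With an EAT effect of 0.2 and none for BMI (n = 100), the mean given entry is 0.238, which is 19% too high. With effects of 0.2 and −0.2 (n = 90), EAT's correlation with LVM change is 0.2 − 0.5 × 0.2 = 0.10, so it usually fails the screen. It is then kept and significant in about 16% of trials, against 36 to 37% for the fixed model.

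**Step 6: the open set of models.** With BMI, waist and waist-hip ratio each in or out, EAT can be adjusted in 2³ = 8 ways. The simulations cover one screened model only, so this freedom is not in the figures above.

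**Step 7: treatment arm.** Suppose EAT and LVM changes are unrelated within arms, and the arms differ by 0.6 to 1.0 SD in EAT change and 0.3 to 0.5 SD in LVM change (assumed). Leaving arm out then makes EAT significant in 7 to 19% of trials at n = 100, against about 5% with arm in the model.

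**The case against.** Four counter-arguments deserve weight.

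- **EAT may be meant to stay in.** Hypothesis 2 is about EAT, and the comparison sentence treats EAT as the variable of interest. If only the other variables are screened, bias in the null settings is about 0.02 with 95% coverage. This stands as a limit, but the text does not settle the reading and the screening sentence makes no exception for EAT. Even with EAT kept, opposite-sign effects of 0.2 and −0.2 give a mean of 0.138 and 91% coverage, although nothing in the documents suggests opposite signs.
- **The unfavourable settings are only part of the range.** The plan cites earlier data in which falls in LVM and EAT were independently related. If that holds with a sizeable effect, the screen does little harm. This also stands.
- **Separate models may be sensible.** Fitting BMI, waist and waist-hip ratio in separate models is reasonable for overlapping measures. That justifies having several models, but not leaving the primary one unnamed.
- **This is a secondary association analysis.** Correct: the between-arm comparisons of EAT and LVM do not use it.

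A reader might infer that the reported EAT coefficient is always biased, that lost confounders are the main cause, or that false-positive claims for EAT become more frequent. The calculations support none of these. Confounders can indeed be dropped, but in the null settings that adds little.

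Screening has no offsetting benefit here: the plan names only four candidate measures for 90 to 100 patients.

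**Conclusion.** The point holds in a limited form. Read literally, the plan reports an adjusted EAT coefficient only after EAT has passed a test in the same data, from a model that is not identified beforehand. With no EAT effect and a weak BMI effect (0.15 to 0.20, correlation 0.5, n = 90), that coefficient averages about 0.13 and its interval covers about 78 to 86%. The main cause is conditioning on EAT's entry. Opposite-sign effects would roughly halve the power to detect EAT.

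These sizes rest on assumed effects and correlations. They fade as effects grow, and almost disappear in the null settings if EAT is always kept. The overall false-positive rate from the screen stays at 3 to 4%. A reader might also infer that the trial's randomised results are at risk; they are not. The change is worth making because it costs almost nothing and the objective's claim about EAT leans on this analysis.

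**What to change.** In Study Hypothesis 2:

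1. Delete the p < 0.1 step.
2. Name one primary model for LVM change that always contains EAT change, one adiposity change chosen now (for example BMI), treatment arm, baseline LVM, age and sex. State the visit and the form of LVM used, since the regression text fixes neither.
3. Report the EAT coefficient with its 95% interval whatever its p-value.
4. Label models with waist or waist-hip ratio in place of BMI as sensitivity analyses.
5. Describe the result as an association unless a mediation analysis is specified in advance.

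The primary model has six terms, which 90 to 100 patients can support without screening. In the two-predictor simulations, keeping both terms fixed gave an unbiased EAT coefficient and about 95% coverage. The cost is a few lines of SAP text. No new data or patients are needed, and less model fitting than is now planned.
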